4. To determine the extent of variation in measles antibodies in women of child bearing age in a population with a long standing measles vaccination program
5. To determine the extent of variation in rubella antibodies in women of child bearing age in a population where rubella vaccine have been recently introduced
6. To determine if variation in antibody levels in infants at 6 months is predominately explained by variation in starting antibody levels in the mother in this population
7. To estimate the half-life of decay of measles and rubella antibodies in infants

Methods:

This study will be an open-label, randomized, 2-arm clinical trial in healthy infants in Bangladesh. 620 children will be enrolled and randomized at 6 months of age to one of two study arms. The study design and participant evaluations are illustrated in Table.

Table: Schematic representation of study arms

Arm		Age of participant				
		6 months	9 months	11 months	Sample size	Enrollment target (sample size + 10% attrition)
A	MR 6 & 9 months	MR •	MR •	•	279	310
B	MR 9 months	•	MR •	•	279	310
Total (infants)					558	620
	Mothers	•			558	620

• Indicates blood collection
MR- Measles -rubella vaccination

Outcome measures/variables:

The primary end-point assessment will be based on **measles antibody titers (mIU/ml) (measured by the multiplex bead assay (MBA))** and rubella titers (IU/mL) (measured by ELISA) on sera collected 8 weeks after completion of vaccination series (at 11 months of age). Immune response is defined at 8 weeks after completion of vaccination series, as seropositivity post-vaccination if pre-vaccination antibody was undetectable (i.e. seroconversion), or a 4-fold or greater increase in antibody titers among pre-vaccination seropositives after adjusting for decline in maternal antibodies. Seroprotection is defined as antibody level of ≥ 120 mIU/mL for measles and >10 IU/mL for rubella. We will calculate the proportion of children attaining post-vaccination protective levels of antibodies.

Description of the Research Project

Hypothesis to be tested

Does this research proposal involve testing of hypothesis: No Yes (describe below)

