For participants in the study group A, the immune response to the 6 month MR dose will be measured at 9 months (blood drawn during the second visit) to evaluate both the proportion seroconverting (from negative to protected), 4-fold or greater increase in antibody titers among pre-vaccination seropositives, after adjusting for decline in maternal antibodies, as well as the magnitude of the immune response (expressed as geometric mean titers of the antibody response). The rate of decay of maternal measles and rubella antibodies will be calculated in infants in arm B based on the difference of antibody levels measured at 6 months (baseline) and 9 months. We will incorporate the model of maternal measles and rubella decay for infants in arm A to measure post-vaccine antibody levels and impact of the maternal

antibody to immune response in infants who had measles or rubella antibodies at enrolment. In the recently published study from Bangladesh, baseline measles virus serum neutralizing antibody seroprotection and anti-rubella virus IgG seroprotection at 9 months of age was low (0.42-1.25% and 0-0.42%, respectively) (21). If during this study, we determine that most children have no detectable levels of maternal measles or rubella antibodies at 6 months it would be impossible to calculate the decay. In this case, we will refer to antibody decay rates reported elsewhere (29, 30).

THE FOLLOWING CHANGES ARE MADE TO THE PROTOCOL:

Since the inception of the project and completion of the field data collection a newer assay, multiplex bead assay (MBA) for measles and rubella has been developed. It has been validated by the CDC measles and rubella laboratories.

Multiplex Bead Assay (MBA) for Serum Antibody Detection of Measles and Rubella

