Multiplex bead assay detects antibodies against viral proteins in the serum of individuals who have been exposed to measles or rubella either by vaccination or natural infection. The MBA works by reading the fluorescent intensity of antigen-specific antibodies in serum binding to antigen coated beads and converting to antibody concentration using a standard curve. This is a novel IgG test for measles and rubella used at research labs. It is not commercially available and requires a significant amount of preparatory work to run the test and is not yet used to diagnose or confirm recent infection (IgM). Developing this capacity is not required for routine measles and rubella surveillance which the Bangladesh National Lab performs. Moreover, icddr,b has no prior experience in running MBA tests.

Measles and Rubella MBA testing will be conducted by the Measles, Mumps, Rubella, and Herpesvirus Laboratory at CDC, a WHO reference laboratory for measles virus. These tests will be performed as described by Smits et al.(31) The analytical cut-off value in the measles MBA assay is 153 mIU/ml. The concentration of antibody \geq 153 mIU/ml will be considered to be protective for measles. The analytical cut-off value in the rubella MBA assay is 9.36 IU/ml. The concentration of antibody \geq 9.36 IU/ml will be considered to be protective for rubella. There may be a formal comparison of rubella IgG concentrations between MBA and the standard EIA results.

Following testing of the samples by MBA, 5%-10% of the samples will also be tested by PRN for quality control testing.

Additional information regarding this assay is included in a detailed protocol maintained at the study laboratory.

Serum Measles IgG Antibody Detected by ELISA

Measles IgG testing will also be conducted by the Measles, Mumps, Rubella, and Herpesvirus Laboratory at CDC.

A commercial enzyme-linked immunosorbent assay (ELISA) will be used for the qualitative detection of IgG antibodies to Measles virus in human serum (Zeus Scientific Inc). Antigen specific antibody in the serum specimen binds to immobilized antigen and is complexed with an antibody linked to an enzyme. The color intensity of the solution depends upon the antibody concentration in the original test sample.

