Immune response is defined as a 4-fold increase in antibody titers 12 weeks after vaccination (post-6-month visit) compared with 6-month pre-vaccine titers accounting for the expected decline in maternal antibody titers or a change from antibody-negative to positive (i.e. seroconversion). In addition, quantitative data on antibody titers will allow us to assess the magnitude of seroresponse show as $-N$ -fold increases of pre- and post-vaccine titers. Seroprotection is defined as titer of ≥ 120 mIU/mL for measles and rubella >10 IU/mL

Secondary outcomes:

Several secondary outcomes will be assessed:

- 1) Secondary outcome is based on measles titers by MBA (mIU/ml) and rubella titers (IU/mL) by ELISA on sera collected 8 weeks after MR 9-month dose of vaccination (i.e., at 11 months) – post two dose series for participants in Arm A and 1 dose for arm B.
- 2) The safety profile of MR vaccine will be assessed by incidence of specific symptoms/problems. They will be categorized into one of the following three categories:
 - a) Immediate reactions (with emphasis on allergic reactions), occurring in the first 30 minutes post vaccination observed by study staff at the fixed site clinic.
 - b) Adverse events (AE) following 6-month MR dose that may occur during the 48 hours after 6-month MR vaccine administration. AEs will be graded and subcategorized as those deemed related to vaccination or not by the investigator.
 - c) Serious adverse events (SAEs) occurring from vaccination during the course of the study, identified or observed by study staff and/or reported by parent at any time during the study period. SAEs will be subcategorized as those deemed related to vaccination or not by the investigator and reviewed by the local Data and Safety Monitoring Board (DSMB) and icddr,b ERC committee.

Data Analysis

This is an open-label trial clinical trial that compares immunogenicity of MR vaccine schedules. The study will recruit 620 participants in 2 arms. Participants will be enrolled at 6 months of age and followed at 9 months and 11 months of age for a total of 5 months of follow-up.

General analytical issues

The data will be analysed by study investigators that include epidemiologists and statisticians. Statistical packages that would be used for the analysis include R, SAS and STATA.

The immunogenicity of each MR vaccination schedule will be determined by measuring antibody levels:

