Some infants in the study will be randomly selected (study arm A) to receive MR vaccine at 6 months, 3 months earlier than the current age (9 months) for MCV1. This will provide early protection against measles and rubella to those infants who seroconvert. All infants will also receive MR vaccine at 9 months as study participants. MR dose scheduled to be administered at 9 months as part of routine immunization will be cancelled. Children then will continue on to receive measles vaccine at 15 months per routine immunization schedule.

During study visits, participants will be examined by study physicians. They will assess infants' growth and development. In addition, participants will be offered advice on diagnosis and treatment of any other illness they experience during the study period. Treatment related cost will be covered by the study.

Potential risks to participants

The potential risks and discomfort to participants stem from blood collections and adverse reactions to MR vaccine.

Immunogenicity of the MR vaccine can only be assessed from testing the blood specimens. Multiple blood draws would be necessary as immunogenicity is measured by determining the change in antibody titers. Moreover, enrolled infants may have maternal antibodies against measles and rubella acquired transplacentally. The first blood draw at 6 months (for infants in both study arms A and B) will establish the baseline maternal antibody titers. The titers are assumed to decay at a fixed rate.

Subsequent blood draws at 9 and 11 months will aid in assessing immunogenicity of MR vaccine as per the primary and secondary objectives. Collecting blood samples from infants in Arm B would help us determine what proportion of infants are additionally protected at 9 months when compared to infants in Arm A. It would also help us determine the rate of background exposure to measles and rubella circulation between 6 and 9 months (only 50% of rubella cases are symptomatic).

The minimal amount of blood necessary for testing is 1 ml. The most common effect of blood draws is pain at the site of collection. In order to minimize the discomfort and risks associated with blood draw, blood from infants will be drawn only by qualified staff experienced in collection of blood in infants. Sterile equipment and technique and alcohol swabs will be used to reduce the risk of infection from blood draw. Pressure will be applied at the site of blood draw to minimize bleeding from the site of blood draw.

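### The 4-fold branch of the response definition covers baseline seropositives in one section and any infant with a detectable titre in others, and no version requires the post-dose value to reach the cut-off

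*Combined protocol and SAP*

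**What the plan says.** Two wordings of the response definition are in force.

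**Restricted.** Special Assays or Procedures covers Arm A at 9 months, after the 6-month dose. It counts seroconversion, "to evaluate both the proportion seroconverting (from negative to protected"), and a "4-fold or greater increase in antibody titers among pre-vaccination seropositives, after adjusting for decline in maternal antibodies". The Project Summary (Outcome measures/variables) has the same limit for the assessment 8 weeks after the last dose. Its first branch is "seropositivity post-vaccination if pre-vaccination antibody was undetectable (i.e. seroconversion"); the wording of its second branch is "or a 4-fold or greater increase in antibody titers among pre-vaccination seropositives after adjusting for decline in maternal antibodies". The background section Seroconversion and immune response repeats the limit.

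**Unrestricted.** Three places read "Immune response is defined as a 4-fold increase in antibody titers 12 weeks after vaccination (post-6-month visit) compared with 6-month pre-vaccine titers" and continue "accounting for the expected decline in maternal antibody titers or a change from antibody-negative to positive (i.e. seroconversion"): Time to endpoint, the Outcome measures/variables text that follows it, and General analytical issues under Data Analysis. Seropositivity at baseline is not mentioned. The two branches are joined by an or, so a 4-fold rise is enough by itself.

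On thresholds, the MBA section says "The analytical cut-off value in the measles MBA assay is 153 mIU/ml" and treats that value as protective. The outcome and analysis sections define measles seroprotection at 120 mIU/mL. For rubella the figures are 10 IU/mL and, by MBA, 9.36 IU/mL. On the decline, Potential risks to participants says "The titers are assumed to decay at a fixed rate", and General analytical issues starts it from the 6-month titre where one can be detected.

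**The concern.** Special Assays or Procedures and the outcome section describe the same arm, dose and visit, so timing does not explain the difference. It concerns infants whose 6-month titre is detectable but below the cut-off. If such an infant rises at least 4-fold, allowing for decline, but stays below the cut-off, the restricted wording calls it a non-responder and the unrestricted wording a responder. The Project Summary adds a gap of its own: its seroconversion branch needs an undetectable baseline and its 4-fold branch a seropositive one, so infants in between fit neither.

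This rule produces the result for primary objective 1. Two analysts could each follow the plan and report different response rates. The broader count would include infants whom the assay still classes as negative, whereas the sample size text and the hypothesis speak of seroconversion.

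**Working it through.** **1. The plan's own figures.** Objective 1 is sized on 50% seroconversion with ±5 points at 0.90 probability: 1.645² × 0.25 / 0.05² = 270.6, so 271; 271 / 0.9 = 301.1, so 302. Both match. The 279 per arm for 75% versus 65% also reproduces (one-sided 5% with continuity correction, neither of which the plan states). These figures rest on assumed proportions, so the definition does not alter them. If, say, 10% of Arm A (28 of 279) were reclassified, 50% would become 40% and the half-width 1.645 × √(0.4 × 0.6 / 271) = 4.9 points.

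**2. The bar set by the 4-fold branch.** Let B be the 6-month titre, h the maternal half-life in days, C the cut-off, and 84 days the interval (12 weeks). The branch is met when the post-dose titre is at least 4 × B × 2^(−84/h). That bar lies below C whenever B < C × 2^(84/h) / 4. The documents give no half-life, so a range is shown.

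| Assumed h | 2^(84/h) | B limit, C = 120 | B limit, C = 153 | B limit, rubella C = 10 | B limit, rubella C = 9.36 |
|---|---|---|---|---|---|
| no adjustment | 1.00 | 30 | 38 | 2.5 | 2.3 |
| 60 days | 2.64 | 79 | 101 | 6.6 | 6.2 |
| 45 days | 3.65 | 109 | 140 | 9.1 | 8.5 |
| 42 days | 4.00 | 120 | 153 | 10.0 | 9.4 |
| 30 days | 6.96 | 209 | 266 | 17.4 | 16.3 |

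**3. Example.** B = 24 and a post-dose value of 96 mIU/mL: 96 / 24 = 4, so the unrestricted branch is met even without adjustment. Yet 96 is below 120 and 153, so under Special Assays or Procedures the infant is neither a baseline seropositive nor a seroconverter.

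**4. The restricted rule.** With B at or above C, the unadjusted bar is at least 480 (C = 120) or 612 (C = 153). It falls below C only if 2^(84/h) > 4, that is h < 42 days; at h = 30 and B = 153 it is 612 / 6.96 = 88. For an 11-month sample on a 6-month baseline (about 150 days) the trigger is 150 / 2 = 75 days.

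**5. Size, by simulation on assumed inputs.** The share at or above the cut-off at 6 months is interpolated from the 1993 Matlab figures under Passive immunity (33% above threshold at 5 months, 5% at 8 months). In normal quantiles that is 0.440 and 1.645, a difference of 1.205 SD over 3 months. At 6 months: 0.440 + 1.205 / 3 = 0.842, or 20%. The half-life is (ln 2 × 91.3) / (1.205 × SD) = 52.5 / SD days; ln-SDs of 0.8 to 1.5 give 66 to 35 days. The vaccine titre has ln-SD 0.8 to 1.5, assay error is 15%, and C = 153. The continuous model sets 50% at or above 153 at 9 months. The all-or-none model assumes a median of 600 mIU/mL in infants who take and about 50% vaccine-positive.

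| Scenario | Unrestricted minus restricted |
|---|---|
| Every infant makes some antibody, all low titres used | 12 to 41 points (37–46% versus 53–86%) |
| Same, decline applied only to baselines at or above 153 | 2 to 18 points |
| Same as the first row, lowest usable titre 60 to 100 mIU/mL | 0 to 9 points |
| All-or-none vaccine take, all low titres used | about 1 to 6 points |
| Nothing below 153 reported | 0 |

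Every extra responder is below 153 after vaccination. The upper ends move by a point or two with the details of the model.

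**The case against.** **Values below 153 may not exist.** The plan calls 153 an analytical cut-off, and its PRNT section uses that term for the lowest dilution tested, as distinct from the interpretive cut-off. In that sense, lower MBA readings would simply be negative and the two wordings would coincide for measles. This stands as a real uncertainty. Against it, MBA reads a concentration from a standard curve, the plan keeps a 120 mIU/mL threshold below 153, and it separates undetectable, detectable and protective levels in mothers. Usable lower values are implied, not stated.

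**The unrestricted branch has an implied limit.** A reader might infer that it is open to every infant. The documents do not support that: the adjustment starts from a detectable 6-month titre. Detectable is not the same as seropositive, so the conflict remains for the infants in between.

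**The size depends on the model.** A reader might infer a gap far beyond the ±5-point precision. That holds only if nearly every infant makes some antibody and every low reading is used. The plan itself describes primary vaccine failure (Study Rationale), which points towards all-or-none take and a much smaller gap. The baseline figures come from a 1993 cohort with an unspecified threshold.

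**The decay adjustment is legitimate.** It is tempting to say that it manufactures responses. But if maternal antibody should have fallen to a quarter, an unchanged reading is evidence of new antibody. The adjustment should stay; what is missing is a floor on the post-dose value.

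**Other outcomes would show the problem.** Seroprotection, geometric mean titres and N-fold rises are to be reported, and seroconversion at 9 months compared between arms. That helps the reader but does not settle which rule is primary.

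**Conclusion.** The contradiction holds on the text and needs no simulation: two rules exist for one primary assessment, and neither puts a post-dose floor on the 4-fold branch. That infants still below the cut-off count as responders follows mainly from the unrestricted wording, and only if concentrations below the cut-off are reported. Under the restricted wording at 12 weeks the problem is small and needs a half-life below about 42 days.

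The size cannot be derived, because the documents give neither a titre distribution nor a half-life. The illustrative range is 0 to 41 points, with about 1 to 6 under all-or-none take. A large bias in the primary result is therefore possible but not established. The sample sizes of 271 and 279 are not affected. This should be fixed; confidence is moderate.

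**What to change.** Before analysis, put one rule in all six places (Project Summary, Seroconversion and immune response, Special Assays or Procedures, Time to endpoint, Outcome measures/variables, General analytical issues):

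- Response means a post-dose concentration at or above the cut-off of the assay used, and either (a) a baseline below that cut-off, or (b) a baseline at or above it with a post-dose value at least 4 times the decay-adjusted baseline, using the infant's actual days between samples.
- Name one cut-off per antigen and assay. Reconcile 120 with 153 mIU/mL for measles, and 10 with 9.36 IU/mL for rubella according to whether ELISA or MBA is used.
- State whether concentrations below the cut-off are reported and how they are handled, including any imputed value.
- Report fold-rises that stay below the cut-off descriptively.
- Apply the same rule to Arm B's unvaccinated 6-to-9-month pairs to show its false-positive rate.

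The cost is wording and a few lines of code; no new samples or tests are needed. The drawback is that the reported response may be lower, and genuine rises below the cut-off no longer count as responses.

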Our study hypothesis is that the proportion of children seroconverting after MR vaccine dose at 9 months following administration of an earlier MR vaccine dose at 6 months of age (Arm A) is not different compared with the immunogenicity obtained when MR vaccine dose is administered at 9 months to infants who have had no previous dose of MR vaccine (Arm B). A secondary hypothesis is the incidence and spectrum of adverse reactions following immunization will be similar between doses given at 6 and 9 months (Arm A), and at 9 months.

The following questions are to be answered by the study:

1. What is immunogenicity of MR vaccine at 6 months of age?
2. What is the impact of the 6-month MR dose on immunogenicity of the 9-month MR dose?
3. What are the frequency and severity of adverse reactions following MR vaccination at 6 months and 9 months?
4. What is correlation between the measles and rubella antibody levels in mothers and level of maternal antibodies in infants

Specific Objectives

Primary objectives

1. To assess immunogenicity of MR vaccine at 6 months of age
2. To assess immunogenicity of MR vaccine at 9 months of age among children without prior measles and rubella vaccination, compared with MR vaccine immunogenicity among those who had a prior MR vaccination at 6 months of age

Secondary objectives:

1. To assess the frequency of adverse reactions following administration of MR vaccine at 6 months
2. To compare the immunogenicity of the MR vaccine first dose administered at 6 months vs at 9 months.
3. To assess the proportion of mothers with undetectable, detectable and protective levels of measles and rubella antibodies

4. To determine the extent of variation in measles antibodies in a convenience sample of women of child bearing age in a population with a long standing measles vaccination program
5. To determine the extent of variation in rubella antibodies in a convenience sample of women of child bearing age in a population where rubella vaccine have been recently introduced
6. To determine if variation in antibody levels in infants at 6 months is predominately explained by variation in starting antibody levels in the mother in this population
7. To estimate the half-life of decay of measles and rubella antibodies in infants

Background

Measles

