Frozen sera will remain frozen during routine shipments to the laboratory at icddr,b and to the CDC measles/rubella laboratory in Atlanta. Shipment of serum will be made according to internationally recognized standards for transport of specimens.

Long-term specimen storage

The parents will be requested to permit storage of blood specimens for no more than 5 years for potential future use in studies. All specimens will be destroyed after 5 years from the end date of the study (the date of last study visit of the last participant to be enrolled). Specimens will be destroyed as per standard procedures of the laboratory for destruction of biohazardous waste.

Sample Size Calculation and Outcome (Primary and Secondary) Variable(s)

Sample size

The study will be powered to address the primary objectives. Sample size calculations are based on equality comparisons with 10% attrition.

Assuming 50% MR seroconversion to a dose at 6 months of age, a sample size of 271 per arm will provide a precision of +/-5% with a 0.90 probability of obtaining an estimate within the desired range. Adjusting for 10% attrition, the enrolment target is 302. Assuming a seroconversion for measles of 75% following a single dose given at 9 months of age, a seroconversion of 65% for a 9 month dose preceded by a 6 month dose, and power of 80%, a sample size of at least 279 per arm is required. Adjusting for 10% attrition, this sample size is inflated to 310. The overall study samples size will be 620 infants. 620 mothers of infants will also be enrolled. (Table)

Time to endpoint (and the corresponding objective)

Primary endpoint

- Time from randomization at 6 months to collection of blood at 9 months of age (To assess immunogenicity of MR vaccine at 6 months of age)
- Time from randomization to collection of blood at 11 months of age (To assess immunogenicity of MR vaccine at 9 months of age among children without prior measles and rubella vaccination, compared with MR vaccine immunogenicity among those who had a prior MR vaccination at 6 months of age)

Secondary endpoint

- Time from randomization 11 months (To assess the frequency of adverse reactions following administration of MR vaccine at 6 months)
- Time from randomization to 11 months of age (To compare the immunogenicity of the MR vaccine first dose administered at 6 months vs at 9 months)

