A major limitation of many studies in which mother-infant paired serum samples were tested, was ascertainment of mothers' past measles or rubella vaccination or measles and rubella natural infection status. Some authors used age (i.e., year of birth, born in pre- measles or rubella vaccination era) as a proxy for determining the past vaccination or disease status. One recent study minimized recall bias as the researchers ascertained mothers' status (vaccine induced or post-infection antibodies) by reviewing their medical charts. [4]

Primary analytical approach

Intention-to-treat (ITT) analysis will be conducted on all enrolled participants who are randomized and receive two measles-rubella vaccines (at 6 and 9 months, study arm A) or one measles-rubella vaccine dose (at 9 months, study arm B).

Children who are seropositive ($\geq 1:120$ mIU/mL) for measles before vaccine administration (at 6 months of age, study arm A; at 9 months, study arm B) will be included in the ITT analyses and will be included in the safety analysis. Similarly, children who are seropositive (≥ 10 IU/mL) for rubella before vaccine administration (9 months of age) will also be included in the ITT analyses.

To evaluate primary and secondary objectives, the analysis will be restricted to participants who

- Have not withdrawn consent for receipt of MR vaccine and follow-up evaluations since enrolment
- Have adequate blood specimen for serological analysis from the enrolment visit, and
- Have adequate blood specimen for serological analysis from study site visits at 6, 9 and 11 months of age (For presence of maternal measles and rubella antibodies – 6 months, seroconversions: 9 months of age and 11 months)

Secondary analytical approach

In addition, we will also perform a per protocol analysis.

To evaluate primary objective, per protocol analysis will be restricted to participants who

- Have not withdrawn consent for receipt of vaccines and follow-up evaluations since enrolment
- Have adequate blood specimen for serological analysis from each visit within 3 days of 6, 9 and 11 months of age, and
- Have received all scheduled vaccines within 3 days of scheduled visit date

Using the above described primary analytical approach we will

- Compare the proportion of participants demonstrating immunogenicity in response to measles and rubella vaccines across study arms and use chi-square test to test for statistical significance across study arms.

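### Non-serious adverse events more than 48 hours after the 6-month dose have no outcome category, although the protocol expects fever and rash after day 7 and records them

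*Combined protocol and SAP*

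**What the plan says.** Secondary objective 1 is the frequency of adverse reactions after the 6-month MR dose. Five parts of the combined protocol and SAP bear on how it is measured.

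- **Time to endpoint, Secondary endpoint:** the line for this objective reads "Time from randomization 11 months (To assess the frequency of adverse reactions following administration of MR vaccine at 6 months".
- **Secondary outcomes, item 2:** of safety events it says "They will be categorized into one of the following three categories". These are (a) immediate reactions in the first 30 minutes; (b) "Adverse events (AE) following 6-month MR dose that may occur during the 48 hours after 6-month MR vaccine administration"; and (c) serious adverse events at any time in the study.
- **Recording, monitoring and reporting of adverse events:** at each visit parents are asked about events since the last visit, and the form takes onset time, severity and relationship. Serious means death, hospitalization or anaphylaxis.
- **Safety monitoring:** fever of 39.4 °C or higher is expected in about 5% to 15% of recipients on days 7 to 12, and rash in about 5%, starting on days 7 to 10. Potential risks to participants lists fever and mild rash among the commonest events at 6 months of age.
- **Data Analysis:** the last bullet under Secondary analytical approach plans an adverse-event comparison by arm and age, with no time window.

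The study questions also ask "What are the frequency and severity of adverse reactions following MR vaccination at 6 months and 9 months".

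On who is analysed, Primary analytical approach says "To evaluate primary and secondary objectives, the analysis will be restricted to participants who" meet listed criteria, one of which is "Have adequate blood specimen for serological analysis from study site visits at 6, 9 and 11 months of age". The intention-to-treat set is limited to infants who are "randomized and receive two measles-rubella vaccines (at 6 and 9 months, study arm A"), or who receive the single 9-month dose in Arm B.

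**The concern.** The delayed febrile and rash reactions that the protocol itself describes are recorded but have nowhere to be counted. If the outcome definition is followed, the reported frequency after the 6-month dose leaves them out. If the endpoint list is followed, whatever was recorded to 11 months is counted. The analysis section does not say which. The note on protocol changes under Special Assays or Procedures indicates that field data collection is complete, so the window could be chosen with the safety data in view.

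The same gap affects the 9-month dose, and the analysis-set rules could remove from the denominator an infant who left because of a reaction. Safety and tolerance at 6 months are among the things that the study says it will deliver.

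**Working it through.** The plan states no figure on this point, so there is none to reproduce. The check sets the sections side by side and then sizes the gap.

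**1. Trace one event: a non-serious fever on day 9 in Arm A.**
- Endpoint list: inside the span from randomization to 11 months.
- Adverse-event recording: asked about at the 9-month visit and entered with onset time.
- Outcome 2(a): no, after 30 minutes.
- Outcome 2(b): no, after 48 hours.
- Outcome 2(c): no, not death, hospitalization or anaphylaxis.
- Result: recorded, within the follow-up span, no category.

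**2. Timing.** Category 2(b) ends at day 2. The fever and rash windows both start at day 7. Overlap is 0 days; the gap is 7 − 2 = 5 days. Milder early fever can still fall in 2(b), and a hospitalized case falls in 2(c).

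**3. Size.** Inputs: 310 infants enrolled in Arm A (sample size section) and the rates in Safety monitoring. Those are rates for vaccine recipients in general; no rate at 6 months is given, so applying them here is an assumption.
- Fever: 310 × 0.05 = 15.5 and 310 × 0.15 = 46.5, so about 16 to 47 infants.
- Rash: 310 × 0.05 = 15.5, so about 16 infants.

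One infant may have both, so the counts should not be added. On the 279 evaluable infants they would be about 14 to 42 and 14.

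**4. The 9-month dose.** Category 2(b) covers the 6-month dose only, and the 9-month visit section rules out a home visit after the 9-month dose. Beyond immediate reactions and serious events, the three categories give no answer on frequency and severity after that dose.

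**5. Recall interval for days 7 to 12 after the 6-month visit.**
- With the 12-week interval in the endpoint section (84 days): 84 − 12 = 72 to 84 − 7 = 77 days, or 10.3 to 11.0 weeks.
- With the three-month return in the enrolment visit section, taken as 13 weeks (91 days): 79 to 84 days, or 11.3 to 12.0 weeks.
- Overall, roughly 10 to 12 weeks.

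**6. Denominator.** The blood rule is stated for primary and secondary objectives, and secondary objective 1 is one of these. The adverse-event bullet sits in a list introduced as using the primary approach. Discontinuation criteria include an allergic reaction to an earlier dose, and Potential risks to participants says that a child with signs of anaphylaxis gets no further MR dose. Such an Arm A infant fails the two-dose condition because of the very event being counted. A safety analysis is mentioned once, without a population.

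**The case against.** The strongest reply is that the endpoint line is only an outer follow-up span. It sits in a list of time spans, its wording is garbled, and serious events under 2(c) also run through the whole study. The 48-hour follow-up is stated consistently wherever it appears. This stands as far as it goes: a reader might infer two rival windows in flat contradiction, and the text does not force that. But under the outer-span reading a late non-serious event still has no category.

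It can also be said that the by-arm analysis is not limited to the three categories. That is fair. A reader might infer that Arm A is never to be compared with Arm B on adverse events, but that comparison is planned; only its window and event set are missing.

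Three further inferences go too far:

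- **That the safety hypothesis sets the 6-month dose against the 9-month dose.** It says that "incidence and spectrum of adverse reactions following immunization will be similar between doses given at 6 and 9 months (Arm A"), and then adds a further mention of 9 months. This can equally mean Arm A's two-dose schedule against a 9-month dose alone. The study question asks for frequency and severity after each dose and compares nothing.
- **That the blood rule costs 31 infants per arm (310 − 279).** That difference is the general attrition allowance, and infants lost before 9 months would not answer the adverse-event question either. In Arm A the 6-month dose is given only after an adequate specimen, so the enrolment specimen should exclude few dosed infants.
- **That 16 to 47 fevers would be recovered by a new category.** Recall is long, and no temperature reading or symptom checklist is stated for the visit question.

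Finally, the blood criteria speak of serological analysis, so they may not be meant for safety. That is plausible, but the plan does not say so.

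**Conclusion.** The point holds as a gap in the outcome definition. Non-serious events after 48 hours following the 6-month dose have no category, and neither do those beyond 30 minutes following the 9-month dose, though the plan records both. The gap covers the whole period in which the protocol expects high fever and rash onset. On its general rates, assumed to apply at 6 months, about 16 to 47 fevers and about 16 rashes per 310 Arm A infants lie outside 2(b), less any hospitalized. How many were in fact recorded cannot be derived from the documents.

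The denominator issue is separate and rests on a literal reading. Its importance lies in direction, since it can remove infants because of a reaction; its size is unknown. Immunogenicity, and the definitions of immediate reactions, 48-hour events and serious events, are unaffected by the missing category. This should be corrected before the safety analysis, but it does not threaten the primary objectives.

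**What to change.** Reconcile the endpoint list, the secondary outcomes, the adverse-event analysis bullet, Safety monitoring and the adverse-event recording section. Then:

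1. Add to outcome 2 a category for non-serious adverse events after 48 hours, by onset date, over a stated window that includes days 7 to 12 after the 6-month visit. Take it from the adverse-event forms at the 9-month visit in both arms. Report the 48-hour home-visit events separately.
2. State that the planned comparison by arm uses this window. Arm B, with no MR dose between 6 and 9 months, supplies the background. Give a risk difference with a 95% CI.
3. Report non-serious events after the 9-month dose from the 11-month form, separately for Arm A (second dose) and Arm B (first dose). Do not pool them: that would mix dose number with schedule.
4. State that the blood and two-dose requirements do not apply to safety. Use all infants dosed for 2(a) to 2(c), and infants with the relevant adverse-event question answered for the new category.

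The cost is outcome and analysis wording; no new visit, procedure or data. The report should state the limits: open-label parental recall of roughly 10 to 12 weeks after the 6-month visit; no stated temperature reading or checklist, so the 39.4 °C threshold may not be identifiable; possible prompting of later reports by Arm A's home visit; and a clear label that the change was made after field data collection.
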